### ***Visit 99***

Visit 99 is only applicable to participants who discontinue the double-blind study treatment prematurely (after Week 36 and before Week 88) and decline to complete the remaining scheduled study visits. These participants will be asked to return for Visit 99 at 88 weeks  $\pm 7$  days (see Section 7.2.1.). This visit is critical to ensure complete data collection for the primary body weight endpoint.

Participants should attend this visit in the fasting state. Procedures to be completed are:

- measurement of weight and waist circumference
- listing of concomitant medications
- assessment of AEs, and
- completion of the Mental Health questionnaires (after the AE assessment).

For participants unwilling to attend this visit, their refusal to attend should be documented in the participant medical record.

### ***Early Discontinuation of Treatment Visit***

Participants unable or unwilling to continue the study treatment for any reason will perform an early discontinuation (ED) of treatment visit (Section 7.2). If the participant is discontinuing during an unscheduled or a scheduled visit, that visit should be performed as an ED visit.

Procedures should be completed according to the SoA. Patient-reported outcomes questionnaires

should be administered as early as possible, as per Suggested Visit Structure (Section 10.8). Administration of Mental Health questionnaires should be after the assessment for AEs.

#### 4.1.1.3. Safety Follow-Up Period

##### *Visit 801*

All participants are required to complete a safety follow-up visit (Visit 801), according to the SoA. Participants discontinuing the study early and performing an ED visit will also be asked to perform the safety follow-up visit (see Section 7.2.1). During the safety follow-up period, participants will not receive study drug. Participants are also required to return any remaining study diaries to the study site at the end of this period.

Visit 801 (safety follow-up visit) should be performed 4 weeks after the last visit in the double-blind treatment period (Visit 24 or Visit 99) or 4 weeks after the ED visit for those who discontinue during the open-label lead-in period or decline to return for Visit 99.

#### 4.1.2. Study Procedures

Participants will perform study procedures listed in the SoA (Section 1.3).

Study participants will be permitted to use concomitant medications that they require during the study, except certain excluded medications (see Section 5.2) that may interfere with the assessment of efficacy and safety characteristics of the study treatments.

Study governance considerations are described in detail in Section 10.1 (Appendix 1).

### 4.2. Scientific Rationale for Study Design

Tirzepatide is a 39-amino acid synthetic peptide with agonist activity at both the GIPR and GLP-1R. Its structure is based on the GIP sequence and includes a C20 fatty diacid moiety (Coskun et al. 2018). It is administered QW by SC injection.

As a dual GIP/GLP-1R agonist, tirzepatide could exceed the efficacy of selective GLP-1R analogs by recruiting metabolically active tissues not targeted by selective GLP-1R analogs (for example, adipose tissue as indicated by the observation of increased energy utilization) (Müller et al. 2018) and has the potential to reach higher efficacy in target tissues, such as insulin-producing pancreatic beta-cells that express both GIPR and GLP-1R, before reaching its therapeutic limitation. Results from a Phase 2 study (GPGB) demonstrated that tirzepatide use in participants with T2DM was associated with a substantial, dose-dependent weight loss, greater than the weight change observed with dulaglutide, a specific GLP-1R agonist. General safety characteristics of all studied doses of tirzepatide were similar to that of the GLP-1R agonist class, consisting mainly of nausea, vomiting, and diarrhea. In general, these events were transient and mild or moderate in severity, with few severe episodes. These data suggest that tirzepatide has the potential to be a pharmacologic treatment for chronic weight management.

Although GI AEs were more common in the 15-mg arm of tirzepatide in the Phase 2 study (GPGB), this dose demonstrated the highest efficacy in terms of weight loss. An optimized dose-escalation regimen proposed in the current Phase 3 study (GPHN) to improve tolerability (and supported by a dose-escalation algorithm from Study GPGF and PK/PD modeling) should enable a use of the 15-mg dose to maximize effects on body weight.

Study GPHN is designed to determine the impact of treatment with MTD of tirzepatide compared with placebo on maintenance of weight loss in participants without T2DM who have obesity or are overweight. Because obesity is a chronic relapsing progressive disease (Bray et al. 2017), the impact of a therapy on weight maintenance in addition to weight loss enables a more complete understanding of its benefit and helps to inform decisions on duration of therapy.

There is not a clear consensus on how best to define weight maintenance, weight regain, or treatment failure. Recently, some studies have attempted to evaluate different measures of weight maintenance and correlate them with clinical outcomes. Berger et al. (2019) analyzed data from over 1500 participants in the Look AHEAD study who had  $\geq 3\%$  initial weight loss, and defined maintenance/regain according to 5 dichotomized cut-offs (0%, 25%, 50%, 75%, and 100%). They correlated different levels of maintenance with cardiometabolic risk factors and found that those who maintained  $\geq 75\%$  of the initial weight loss had the most cardiometabolic benefit. Conducting a similar study in a bariatric surgery cohort, which experienced much greater initial weight loss than the Look AHEAD cohort, King et al. (2018) found that 20% or greater regain correlated the same or better than other cut-offs with most cardiometabolic risk factors. Based on these recent data, maintaining 75% to 80% of initial weight loss regardless of therapeutic modality appears to be clinically relevant. That being said, it does not seem reasonable to define therapeutic failure at the same cut-off. Perhaps a more appropriate definition of complete therapeutic failure is regaining weight to the point that an individual falls below the 5% weight loss threshold which is used to define initial success of treatment in the first place. To have a more complete picture of therapeutic benefit, an evaluation of both maintenance (at an 80% threshold of maximum weight loss) and time to complete failure (defined as returning to  $>95\%$  of initial weight) is likely warranted. Therefore, both these measures are being evaluated in the randomized weight-maintenance phase of Study GPHN.

A double-blind design after 36 weeks (randomization) was selected to minimize participant and investigator bias in assessments for efficacy, safety, and study drug tolerability. In addition, the objective of Study GPHN is to evaluate maintenance of initial weight loss, and therefore, achieving a near-maximum weight loss effect and body weight plateau prior to randomization is important. Thirty-six weeks was chosen as the time point for randomization based on PK/PD modeling which shows that by 36 weeks (including 20-week dose escalation) most participants will reach a near-plateau of body weight.

A placebo comparator was selected for this trial in accordance with regulatory guidance (FDA 2007; EMA 2016). In addition, all participants, regardless of treatment assignment, will receive lifestyle-modification counseling consistent with current guidelines for weight management (Jensen et al. 2014). Specifically, participants will consult with a dietitian, or equivalent qualified delegate, throughout the study to achieve an approximately 500 kcal/day energy deficit through a combination of caloric restriction and increased physical activity (see Section 5.3).

The planned duration of treatment for the primary endpoint at 88 weeks allows for a 52-week treatment period at the dose achieved following dose escalation to either 10 mg or 15 mg. This duration is considered appropriate to assess the full effects and balance of risk and benefit for tirzepatide MTD compared with placebo on body weight and is consistent with regulatory guidelines (FDA 2007; EMA 2016).

The effects of study intervention cessation will be assessed in the 4-week safety follow-up/observational period. To minimize the potential confounding effect of changes to

concomitant medications, participants will be permitted to use concomitant medications that do not interfere with the assessment of efficacy or safety characteristics of the study treatments.

#### 4.3. Justification for Dose

Tirzepatide MTD (10 mg or 15 mg QW) will be evaluated in this study. These doses and associated escalation schemes were selected based on assessment of safety, efficacy (weight loss), and GI tolerability data in Phase 1 and 2 studies in patients with T2DM, followed by exposure-response modeling of the data that predicted weight loss in patients with overweight or obesity.

In a 26-week, Phase 2 study (GPGB) of participants with T2DM, tirzepatide reduced body weight by 4.8 kg, 8.7 kg, and 11.3 kg at dose levels of 5, 10, and 15 mg, respectively, whereas the weight loss observed in participants on dulaglutide, a selective GLP-1R agonist, used at the dose of 1.5 mg, was 2.7 kg (Frias et al. 2018).

Similar to the GLP-1R agonist class, most of the tirzepatide AEs were dose-dependent and GI-related, consisting mainly of nausea, vomiting, and diarrhea. In general, these events were mild or moderate in severity, with few severe episodes, and transient.

Tirzepatide doses of 10 mg and 15 mg were selected based principally on the following criteria:

- each dose provides robust weight loss relative to placebo
- the percent of patients achieving  $\geq 10\%$  is higher with 15 mg than 10 mg, and
- safety and tolerability were supported by Phase 2 results and/or PK/PD modeling.

Dosing algorithms starting at a low dose of 2.5 mg accompanied by dose escalation of 2.5-mg increments every 4 weeks should permit time for development of tolerance to GI events and are predicted to minimize GI tolerability concerns. The maximum proposed dose of 15 mg maintains an exposure multiple of 1.6 to 2.4 to the no-observed adverse effect level doses in 6-month monkey and rat toxicology studies.

#### 4.4. End of Study Definition

Section 7.2 describes the criteria used to determine if a participant has completed the study.

The end of the study is defined as the date of the last visit of the last participant in the study or last scheduled procedure shown in the SoA for the last participant in the trial globally.

## 5. Study Population

Prospective approval of protocol deviations to recruitment and enrollment criteria, also known as protocol waivers or exemptions, is not permitted.

### 5.1. Inclusion Criteria

Participants are eligible to be included in the study only if all of the following criteria apply:

#### Type of Participant and Disease Characteristics

1. Have a BMI of:
  - $\geq 30 \text{ kg/m}^2$  or
  - $\geq 27 \text{ kg/m}^2$  and previously diagnosed with at least 1 of the following weight-related comorbidities:
    - Hypertension: treated or with systolic blood pressure  $\geq 130 \text{ mmHg}$  or diastolic blood pressure  $\geq 80 \text{ mmHg}$
    - Dyslipidemia: treated or with low-density lipoprotein (LDL)  $\geq 160 \text{ mg/dL}$  (4.1 mmol/L) or triglycerides  $\geq 150 \text{ mg/dL}$  (1.7 mmol/L), or high-density lipoprotein (HDL)  $< 40 \text{ mg/dL}$  (1.0 mmol/L) for men or HDL  $< 50 \text{ mg/dL}$  (1.3 mmol/L) for women
    - Obstructive sleep apnea
    - Cardiovascular disease (for example, ischemic cardiovascular disease, New York Heart Association [NYHA] Functional Classification Class I-III heart failure)
2. Have a history of at least 1 self-reported unsuccessful dietary effort to lose body weight
3. In the investigator's opinion, are well-motivated, capable, and willing to:
  - learn how to self-inject study drug, as required for this protocol (visually impaired persons who are not able to perform the injections must have the assistance of a sighted individual trained to inject the study drug; persons with physical limitations who are not able to perform the injections must have the assistance of an individual trained to inject the study drug)
  - inject study drug (or receive an injection from a trained individual if visually impaired or with physical limitations)
  - follow study procedures for the duration of the study, including, but not limited to, following lifestyle advice (for example, dietary restrictions, exercise plan), maintaining a study diary, and completing required questionnaires

#### Participant Characteristics

4. Are at least 18 years of age and age of majority per local laws and regulations

- a. Male participants:
  - Male participants with partners of childbearing potential should be willing to use reliable contraceptive methods throughout the study and for 5 half-lives of study drug plus 90 days, corresponding to 4 months after the last injection
- b. Female participants:
  - Female participants not of childbearing potential may participate and include those who are:
    - infertile due to surgical sterilization (hysterectomy, bilateral oophorectomy, or tubal ligation) or congenital anomaly (such as Mullerian agenesis)  
**or**
    - Postmenopausal – defined as either:
      - A woman at least 40 years of age with an intact uterus, not on hormone therapy, who has cessation of menses for at least 1 year without an alternative medical cause AND a follicle-stimulating hormone (FSH)  $\geq 40$  mIU/mL; women in this category must test negative in pregnancy test prior to study entry  
**or**
      - A woman 55 or older not on hormone therapy, who has had at least 12 months of spontaneous amenorrhea  
**or**
      - A woman at least 55 years of age with a diagnosis of menopause prior to starting hormone replacement therapy
  - Female participants of childbearing potential (not surgically sterilized and between menarche and 1-year postmenopausal) must
    - test negative for pregnancy at Visit 1 based on a serum pregnancy test
    - if sexually active, agree to use 2 forms of effective contraception, where at least 1 form is highly effective for the duration of the trial plus 30 days, corresponding to 2 months after the last injection, and
    - not be breastfeeding

**Note:** Contraceptive use by men or women should be consistent with local regulations regarding the methods of contraception for those participating in clinical studies.

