Serum pregnancy		X																										
	For women of childbearing potential only																											
Urine pregnancy (local)		X			X			X			X				X			X			X			X		X	X	
	A urine pregnancy test must be performed at Visit 2 with the result available prior to first injection of study drug(s) for women of childbearing potential only. Additional pregnancy tests (beyond those required per the SoA) should be performed at any time during the trial if a menstrual period is missed, there is clinical suspicion of pregnancy, or as required by local law or regulation.																											
Follicle-stimulating Hormone (FSH)	X																											
	Follicle-stimulating hormone test is to be performed at Visit 1 for postmenopausal women at least 40 years of age with an intact uterus, not on hormone therapy, and who have had spontaneous amenorrhea for more than 1 year without an alternative medical cause.																											
Calcitonin	X				X			X			X														X		X	X
Pancreatic amylase	X				X			X			X														X		X	X

Visit	1	2	3	4	5	6	7	8	9	10	11	12	13	14	15	16	17	18	19	20	21	22	23	24	99	ED	801
Week of Treatment	-2	0	4	8	12	16	20	24	28	32	36	40	44	48	52	56	60	64	68	72	76	80	84	88	88		4 wks post end of TxP
Allowable Interval Tolerance (days)		±3	±3	±3	±3	±3	±3	±3	±3	±3	±3	±3	±3	±3	±3	±3	±3	±3	±3	±3	±3	±3	±3	±3	±7	±7	±3
Fasting Visit	X	X	X	X	X	X	X	X	X	X	X	X		X			X		X		X		X	X	X	X	
Telephone Visit													X	X		X	X		X	X		X	X				
Lipase	X				X			X			X													X		X	X
Urinary albumin/creatinine ratio	X										X													X		X	X
Cystatin-c	X										X													X		X	X
Thyroid-stimulating hormone (TSH)	X																										
Immunogenicity (includes PK sample)		X	X		X			X			X			X					X			X		X		X	X
In the event of systemic drug hypersensitivity reactions (immediate or nonimmediate), additional unscheduled samples should be collected as detailed in Section 8.3.2.7 (Hypersensitivity Reactions). Immunogenicity samples and PK samples for immunogenicity must be taken prior to drug administration.																											
Stored Samples																											
Pharmacogenetic sample			X																								
Nonpharmacogenetic sample			X			X			X			X												X		X	X
Randomization and Dosing																											
Randomization														X													
Dispense study intervention(s)			X	X	X	X	X	X	X	X	X	X	X	X	X			X			X		X				
Observe participant administer study intervention(s)			X																								

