## 10.5. Appendix 5: Contraceptive Guidance and Collection of Pregnancy Information

### Definitions:

#### Woman of Childbearing Potential

A woman is considered fertile following menarche and until becoming postmenopausal unless permanently sterile (see below).

If fertility is unclear (for example, amenorrhea in adolescents or athletes) and a menstrual cycle cannot be confirmed before first dose of study intervention, additional evaluation should be considered.

Women in the following categories are not considered women of childbearing potential:

Article I. Premenarchal

Article II. Premenopausal female with 1 of the following:

- Documented hysterectomy
- Documented bilateral salpingectomy
- Documented bilateral oophorectomy

For individuals with permanent infertility due to an alternate medical cause other than the above (for example, Mullerian agenesis, androgen insensitivity), investigator discretion should be applied to determining study entry.

**Note:** Determination can come from the site personnel's review of the participant's medical records, medical examination, or medical history interview.

Article III. Postmenopausal female

- A postmenopausal state is defined as either
  - A woman at least 40 years of age with an intact uterus, not on hormone therapy, who has cessation of menses for at least 1 year without an alternative medical cause, AND an FSH  $\geq 40$  mIU/mL; or
  - A woman 55 or older not on hormone therapy, who has had at least 12 months of spontaneous amenorrhea; or
  - A woman at least 55 years of age with a diagnosis of menopause prior to starting hormonal replacement therapy (HRT).
- Females on HRT and whose menopausal status is in doubt will be required to use 1 of the nonestrogen hormonal highly effective contraception methods if they wish to continue their HRT during the study. Otherwise, they must discontinue HRT to allow confirmation of postmenopausal status before study enrollment.

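### Section 5.1 exempts a premenopausal woman with tubal ligation only, Appendix 5 by omission does not, and the schedule does not say which definition governs her urine pregnancy tests.

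*Protocol*

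**What the plan says.** Three places in the protocol bear on this woman.

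- **Section 5.1, Participant Characteristics.** Women not of childbearing potential include those who are "infertile due to surgical sterilization (hysterectomy, bilateral oophorectomy, or tubal ligation". Women of childbearing potential are those "not surgically sterilized and between menarche and 1-year postmenopausal". The latter must have a negative serum pregnancy test at Visit 1 and must, "if sexually active, agree to use 2 forms of effective contraception, where at least 1 form is highly effective", for the length of the trial and a period after it.
- **Appendix 5 (Section 10.5), Woman of Childbearing Potential.** The general rule is: "A woman is considered fertile following menarche and until becoming postmenopausal unless permanently sterile (see below". The surgical entries that follow for premenopausal women are hysterectomy, "Documented bilateral salpingectomy" and bilateral oophorectomy. Tubal ligation is not among them. For permanent infertility from another medical cause, "investigator discretion should be applied to determining study entry".
- **Section 1.3, Schedule of Activities.** The Visit 2 urine test is required "with the result available prior to first injection of study drug(s) for women of childbearing potential only". Extra tests are to be done "if a menstrual period is missed, there is clinical suspicion of pregnancy, or as required by local law or regulation". The note cites neither Section 5.1 nor Appendix 5.

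Appendix 2 (Section 10.2) does point to Section 5.1 on pregnancy testing, but only for the screening criteria.

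**The concern.** The schedule's test requirement depends on a term that the protocol defines twice, and the two definitions give different answers for one identifiable kind of participant. A site that reads Section 5.1 does no scheduled urine test on her. A site that reads Appendix 5, the only headed definition of the term, tests her throughout. Both can say that they followed the protocol.

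What is at stake is a pregnancy safeguard. Every enrolled participant receives tirzepatide in the open-label period, and the Week 0 urine test is the last check before the first dose. Section 5.1 asks for a negative pregnancy test before entry even from a woman of 40 or older with a year without menses and an FSH of at least 40 mIU/mL. It asks for none from a premenopausal woman with tubal ligation.

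**Working it through.** The plan gives no figure on this point, so the check compares the texts and then counts the tests.

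**Step 1. Classification of a premenopausal woman with tubal ligation only**

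| Source | Rule | Result |
|---|---|---|
| Section 5.1 | Tubal ligation named as surgical sterilization | Not of childbearing potential, expressly |
| Appendix 5 | Fertile unless permanently sterile; surgical list omits tubal ligation | Of childbearing potential, by default |
| Schedule note | Tests limited to women of childbearing potential | No definition cited |

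The two surgical lists name four procedures between them. Two appear in both: hysterectomy and bilateral oophorectomy. Tubal ligation appears only in Section 5.1 and bilateral salpingectomy only in Appendix 5. Bilateral salpingectomy raises no conflict, because the phrase about surgical sterilization in Section 5.1 can cover it. Only tubal ligation does.

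**Step 2. Does any text settle which definition applies to the on-study tests?**

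- The Appendix 5 list is not introduced as a set of examples, so it reads as closed.
- Its discretion clause deals with other medical causes, illustrated by Mullerian agenesis and androgen insensitivity, and concerns study entry. It does not reach tests after entry.
- The Appendix 2 cross-reference to Section 5.1 is limited to screening.

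None of these settles the on-study tests.

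**Step 3. Scheduled urine tests for a completer**

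The urine row is marked at Visits 2, 5, 8, 11, 15, 18, 21, 24, ED and 801. The ED mark applies only to those who stop early, so a completer has:

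- before the first injection: Visit 2 (Week 0) = 1
- during treatment: Weeks 12, 24, 36, 52, 64, 76, 88 = 7
- safety follow-up: Visit 801 = 1
- total: 1 + 7 + 1 = 9

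If Appendix 5 governs she has 9. If Section 5.1 governs she has 0.

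**Step 4. Are these visits already office visits?**

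The eight telephone visits are 13, 14, 16, 17, 19, 20, 22 and 23 (Weeks 44, 48, 56, 60, 68, 72, 80 and 84). Their overlap with the urine-test visits is 0.

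**The case against.** The strongest reply is that Section 5.1 speaks to this woman's case and Appendix 5 is silent, so the express rule should control. Section 5.1 is also not confined to entry, since its contraception condition runs through the trial. Appendix 5 counts vasectomy as a highly effective method but does not list tubal ligation as a method at all, which suggests that the authors already regarded ligation as sterilization. And a ligated woman who misses a period is tested under either reading.

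Much of this stands. Letting Section 5.1 control is a reasonable reading, and Appendix 5 reaches the other result by omission rather than by statement. But Appendix 5 has a default rule as well as a list, and under that rule the omission has a consequence. Nothing says which definition the schedule uses. The extra-test provision covers a missed period, clinical suspicion and legal requirements; unless local law requires a test, it does not replace a routine test before the first dose.

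A reader might infer that the contraception duty is equally open, with either no method or two required of her if she is sexually active and not abstinent. The documents do not support that. Section 5.1 states its own two-method rule for the length of the trial and limits it to women who are not surgically sterilized. The two-method sentence in Appendix 5 stands under general guidance and does not itself say which women it covers.

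A reader might also infer that a pregnancy in such a woman would go unmanaged. It would not: Sections 7.1 and 7.2 and Appendix 5 require stopping study drug and withdrawal from the study.

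**Conclusion.** The point holds as a wording inconsistency in a pregnancy safeguard. For a premenopausal woman with tubal ligation only, two definitions in the current protocol cannot both apply, and the schedule does not choose between them. The size is 0 against 9 scheduled urine tests per completer, including the one before the first injection.

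This rests on reading the Appendix 5 list as closed and on the urine-row marks at the columns where they stand. A misplaced mark would change a week label, not the total.

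The importance is minor. The documents do not say how many such women would enrol and give no pregnancy rate after ligation, so no number of affected participants and no expected benefit can be stated. No endpoint, estimand or power calculation is affected.

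**What to change.** Have the urine-test note in the Schedule of Activities cite the Appendix 5 definition, so that women with tubal ligation only have the scheduled tests. In Section 5.1, add that for pregnancy testing these women are treated as Appendix 5 defines them. Leave the contraception condition in Section 5.1 as it is unless the sponsor decides to change it, and say so, so that the testing change is not read as a new contraception duty.

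The cost is wording in two places and nine urine tests per affected completer, all at office visits already scheduled. If the alignment in Section 5.1 extends to the screening serum test, add one test at Visit 1, where blood is already drawn for eligibility.

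Adding tubal ligation to the exempt list in Appendix 5 would also remove the inconsistency and would add no tests. It brings no safety gain, however, and would leave her with no scheduled pregnancy test.
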